4.7. Costs: N/A

4.8. Safeguards for Protecting Information:

The research consents will be stored in a locked cabinet in a locked room. Medical records will be annotated with ICD-10 code Z00.6 to reflect the subject's participation in a research study. All research data including patient demographics will be kept in an electronic database, which will be encrypted, double password protected and the access will be restricted. The research data will be de-identified and any links to identifiable data will be destroyed as soon as possible. The research data will not be utilized for further research activity beyond the protocol stipulations without additional IRB approval.

4.9. Safeguards for Protecting Subjects:

The principal investigator will be responsible for the protocol safety monitoring. The PI will make study documents (e.g., consent forms, data pulls) and pertinent hospital or clinical records readily available for inspection by the local IRB and oversight staff for confirmation of the study data.

4.9.1. Minimizing Risks:

If a subject experiences any injury, adverse event, or unexpected clinical finding, a PI, AI, or Primary Care provider will be available to assess the subject and initiate proper clinical care

4.9.2. Vulnerable Populations: N/A

4.9.3. Clinical Care:

If a subject experiences any injury, adverse event, or unexpected clinical finding, a PI, AI, or Primary Care provider will be available to assess the subject and initiate proper clinical care.

4.9.4. Injury Compensation: N/A

4.9.5. Data Safety Monitoring:

The trial will be conducted in compliance with this protocol, International Conference on Harmonization (ICH) Guidelines for Good Clinical Practice (GCP), and any applicable national and international regulatory requirements. The principal and associate investigators will be monitoring all aspects of the study in accordance with the appropriate regulations and will have regular meetings with periodic quality control of data documentation and collection. The objectives of the monitoring meetings will be:

- 1) To verify the prompt reporting of all data points, including reporting Serious Adverse Events (SAEs) and checking availability of signed informed consent,
- 2) To compare individual subject records, data pulls and/or the study source documents/case report forms (supporting data, laboratory specimen records and medical records to include physician progress notes, nurses' notes, subjects' hospital charts),
- 3) To ensure protection of study subjects, compliance with the protocol, and accuracy and completeness of records.

The principal investigator will be responsible for the protocol safety monitoring. The PI will make study documents (e.g., consent forms, data pulls) and pertinent hospital or clinical records readily available for inspection by the local IRB and oversight staff for confirmation of the study data.

[name], DO, Maj (Primary) and [name], Capt (Alternate) will be the research monitors assigned to this study.

5.0. Alternatives: The alternative is not to participate in this study.

6.0. Data Analysis:

6.1. Outcome Measures:

We will be utilizing stratified random sampling with proportionate allocation which will ensure that all parts of the population are represented in the sample.

Factors:

1. Subject Characteristics
 - a. Subject identification: nominal variable (1 ... n)
 - b. Gender: binomial variable (male, female)
 - c. Age: interval variable (years)
 - d. Height: interval variable (inches)
 - e. Weight: interval variable (pounds)
2. Treatment: nominal variable (Naproxen + MSM, Naproxen + placebo)
3. Time (5 repeated measures for each subject): nominal variable (0wk, 4wk, 8wk, 12wk, 16wk)
4. Outcomes
 - a. VAS: interval variable ^{72,73} (1-10 cm)
 - b. RMDQ: interval variable (0-11,18, or 24 depending on instrument used)
 - c. PIQ-6: interval variable (20-80)

6.2. Sample size estimation/power analysis:

The power for the rANCOVA was assessed using G*Power Version 3.0.10 ⁷⁶. The investigators anticipate there will be large effect size as determined by a 50% improvement in clinical outcomes. The results shown below indicate 34 subjects per Treatment group with 5 repeated measures will achieve a power of 0.80 to detect a large effect size of 0.40 at $\alpha = 0.05$.

Input:

Effect size f	= 0.4
β/α ratio	= 4
Total sample size	= 68
Number of groups	= 2
Repetitions	= 5

Corr among rep measures	= 0.8
Output:	
Critical F	= 2.524097
Numerator df	= 4.000000
Denominator df	= 63.000000
α err prob	= 0.049538
β err prob	= 0.198150
Power (1- β err prob)	= 0.801850

Software R Version 2.13.1 (R Foundation for Statistical Computing)⁷⁷

6.3. Statistical Analysis:

Descriptive statistics: Sample means, standard deviations and standard errors of measurement for interval variables and frequency distributions for nominal variables will be calculated for the total sample and for the Treatment groups.

Hypothesis Testing: H_{01} and H_{02} : interval outcome data will be tested by a mixed effects repeated measures analysis of covariance (rANCOVA)

Post Hoc Tests: In the event H_{02} is rejected, contrasts will be used to investigate differences among means.

6.4 Number of Subjects:

Number of subjects planned for NELLIS AFB	Enrolled in Study	100	to result in	68	completing the study.
TOTAL NUMBER OF SUBJECTS (nation-wide/study-wide): 100					

7. Duration of Study: Approximate duration of the study: 2 years

8. Local and External Support Services: None

9. Intramural (GME) and Extramural Funding Support:

This study will be sponsored by Bergstrom Nutrition. The collaborative research will be executed in accordance with 15 USC 3710a through a Cooperative Research and Development Agreement, between the 99th MDG and Bergstrom Nutrition. The estimated fair market value of the support is \$17,570.00. We received a grant from AFMSA/SG5 in the amount of \$50,000 in support of purchasing supplies and a research coordinator.

10. Conflict of Interest: None

a. **Financial Conflict of Interest:** No financial conflicts of interest exist.

b. **Personal Conflict of Interest:** No personal conflicts of interest exist.

c. **Current Off-Duty Employment:** None

11. Use of an Investigational New Drug, use of a Drug for a non-FDA approved purpose, use of an investigative device or use of a placebo:

This research uses an Investigational New Drug

[x] YES [] NO

This research uses a FDA approved drug for a non-FDA approved purpose

[] YES [x] NO

This research uses an Investigational Device

[x] YES [x] NO

This research uses a placebo.

[x] YES [] NO

12. Medical Research Area for the Study: (Pick as many as appropriate)

 Analytical Chemistry	 Anatomy	 Anesthesiology	 Biochemistry
 Cardiovascular Surgery	 Cardiology	 Cell Biology	 Dentistry
 Dermatology	 Dietetics	 Electrophysiology	 Endocrinology
 Emergency medicine	 Gastroenterology	 General Surgery	 Hematology
 Histology	 Immunology/Allergy	 Infectious Disease	 Microbiology
 Molecular Biology	 Neonatology	 Neurology	 Neurosurgery
 Nursing	 OB/GYN	 Occupational Medicine	 Occupational Therapy
 Oncology	 Ophthalmology	 Oral/Maxillofacial Surgery	 Orthopedics
 Pathology	 Pediatrics	 Pharmacology	 Physical Therapy
 Mental Health	 Radiology/Imaging	 Urology	 Wellness
 Other (state):			

13. Attachments:

1. Certificate of Compliance
2. Informed Consent Document
3. HIPAA Authorization Document
4. Use of an Investigational New Drug (IND) in Research
5. Use of a Placebo in Research
6. Intramural and Extramural Funding Support Appendix
7. FDA Correspondence
8. Pharmacy Letter of Support
9. Laboratory Letter of Support
10. Pain Impact Questionnaire
11. Roland Morris Disability Questionnaire
12. Study Medication Diary
13. Form A2-Study Personnel

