Document Date: 4/5/2018

The use of Methylsulfonylmethane (MSM) in the treatment of low back pain.

NCT02268305

**PROTOCOL FOR CLINICAL INVESTIGATION – NON-EXEMPT HUMAN
(Wilford Hall Ambulatory Surgical Center – WHASC)**

PROTOCOL SUMMARY

1. Title:

The use of Methylsulfonylmethane (MSM) in the treatment of low back pain.

FWH20140075H

2.0. Principal Investigator (PI):

NELLIS AFB PI:

Name	[name]
Rank/Corps or Civilian Rating	Col, USAF, MC
Date of IRB Approved CITI Training & Date of Good Clinical Practice Training	12/28/2017
Branch of Service	USAF
AD Mil/DoD Civilian/Ctr/Non-DoD Civ	AD
Department & Base	Department of Medical Education, Nellis AFB
Phone & [contact]
E-Mail Address & AKO/DKO E-Mail Address	[contact]

3.0. Research Plan:

3.1. Purpose:

The purpose of this study is to assess whether Methylsulfonylmethane (MSM) plus standard of care naproxen improves symptoms of lower back pain versus standard of care naproxen plus placebo.

3.2. Hypotheses, Research Questions or Objectives:

Does the addition of MSM to standard of care treatment improve symptoms of lower back pain assessed by the Roland-Morris Disability Questionnaire (RMDQ) and Pain Impact Questionnaire (PIQ-6)?

4. Brief Summary of the study:

We are studying whether MSM plus standard of care naproxen improves symptoms of lower back pain compared to standard of care naproxen plus placebo. Subjects will be randomized into 1 of 2 groups. Group 1 will take by mouth 6000 milligrams (mgs) of MSM plus standard of care naproxen. Group 2 will take by mouth placebo capsules plus standard of care naproxen. Subjects will be instructed to take their study pills for 12 weeks and record on a study diary. They will then be followed up for one final visit 4 weeks later. RMDQ, PIQ-6, pain level, comprehensive metabolic panel (CMP), complete blood count (CBC) will be assessed at 4 week intervals for 12 weeks. Subjects' participation will last 16 weeks.

5. Subjects:

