Proposal of Materials and Methods: Selection of proper follow up time has been based on studies of MSM in osteoarthritis. Follow up time ranges from 2¹³ to 12 weeks¹². In the study by Kim et al¹³, efficacy was not noted until 4 weeks into the study. This improvement was even more notable at 8 and 12 weeks than at 4 suggesting that improvement in symptoms may require longer exposure MSM. For this reason, the impact MSM on low back pain, function and quality of life should be carried out to at least 12 weeks.

The use of 4 week intervals for reassessment mirrors the protocol by Kim et al. This is convenient considering the PIQ-6/R was designed for a 1 (acute) or 4 week (chronic) follow up.

Inclusion and Exclusion Criteria for this study will be similar to the common criteria from various studies on Low Back Pain^{42-44,52,55,58,61}.

Studies of MSM and osteoarthritis have recommended MSM dosing ranging from 500mg TID to 3 g BID^{12,13}. Doses of 6 g daily are considered safe^{13,24}. As noted above, studies in rats found that doses 5-7 times the maximum recommended daily amount may be given without any appreciable toxicity^{15,68}. Human studies using >6gm/day have not been performed. MSM will be given in the dose of 1500mg x2 Tabs, BID. Standard of care naproxen is typically defined as a dose of 225-550 mgs twice a day although it may vary depending on the provider.

3.5.1. Bibliography:

3. Teets RY, Dahmer S, Scott E. Integrative Medicine Approach to Chronic Pain.
5. Ernst E. Prevalence of use of complementary/alternative medicine: a systematic review. *Bull World Health Organ [online].* 2000; 78(2) 258-266

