- Subjects will be asked “On a scale of 0-10, with 10 being the worst pain, what is your current level of pain”.
- Research staff will record whether subject had any side effects to report.
- Subjects will have their study medications refilled.
- Research staff will collect the subject’s Study Diary, issue them a new one, and remind them to bring it with them to the next study visit.
- Research staff will remind subjects to take the pills as instructed and to return the bottle to the research staff at the next visit.
- Subjects will have the following research-driven blood test drawn via 1 venipuncture (5-10 mls, approximately 1-2 teaspoons of blood drawn for each test) which include:
 - Comprehensive metabolic panel (liver function, renal function, plasma glucose tests).
**Subjects who have had a comprehensive metabolic panel test within the one week prior to this visit will not need to have this test repeated unless they are abnormal.*
 - Complete Blood Count.
**Subjects who have had a complete blood count test within the one week prior to this visit will not need to have this test repeated unless they are abnormal.*

Visit 4/Week 12 *SUBJECTS STOP TAKING STUDY PILLS AT THIS VISIT:

- Record: Weight (in pounds), blood pressure, history of lower back surgeries, medical history, and concomitant medications.
- Subjects will be asked to complete the following questionnaires:
 - RMDQ
 - PIQ-6
- Subjects will be asked “On a scale of 0-10, with 10 being the worst pain, what is your current level of pain”.
- Research staff will record whether subject had any side effects to report.
- Research staff will collect the subject’s Study Diary.
- Research staff will collect the study pills.
- Subjects will have the following research-driven blood test drawn via 1 venipuncture (5-10 mls, approximately 1-2 teaspoons of blood drawn for each test) which include:
 - Comprehensive metabolic panel (liver function, renal function, plasma glucose tests).
**Subjects who have had a comprehensive metabolic panel test within the one week prior to this visit will not need to have this test repeated unless they are abnormal.*
 - Complete Blood Count.
**Subjects who have had a complete blood count test within the one week prior to this visit will not need to have this test repeated unless they are abnormal.*

Final Visit 5/Week 16:

- Record: Weight (in pounds), blood pressure, history of lower back surgeries, medical history, and concomitant medications.

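### Sections 6.1 to 6.3 define no on-treatment contrast for MSM, list weeks 0 and 16 beside the treated visits, and print a power that fits neither two-group test

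*Combined protocol and SAP*

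**What the plan says.** Section 6.1, Factor 3, reads "Time (5 repeated measures for each subject): nominal variable (0wk, 4wk, 8wk, 12wk, 16wk". Weeks 0 and 16 are therefore levels of the repeated response on the same footing as weeks 4, 8 and 12.

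Week 0 comes before treatment: study pills are first handed out at Visit 1, where the baseline assessments are made (3.6, 3.6.7). Week 16 comes after it: the Visit 4/Week 12 heading in 3.6 states "SUBJECTS STOP TAKING STUDY PILLS AT THIS VISIT". Item 4 of the Protocol Summary keeps the periods apart. Outcomes "will be assessed at 4 week intervals for 12 weeks", and of subjects it says "They will then be followed up for one final visit 4 weeks later".

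Section 6.3 says of H01 and H02 that "interval outcome data will be tested by a mixed effects repeated measures analysis of covariance (rANCOVA") and that, if H02 is rejected, "contrasts will be used to investigate differences among means". Neither hypothesis is defined anywhere, no covariate is named, and no visit or contrast carries the treatment comparison. Section 6.2 states that "34 subjects per Treatment group with 5 repeated measures will achieve a power of 0.80".

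**The concern.** The research question is whether MSM, taken for 12 weeks, improves symptoms. At week 0 the expected difference between arms is zero by randomisation. At week 16 nobody is taking study pills. A test that gives these two visits the same weight as the treated ones does not answer that question directly.

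At least three tests fit the wording: a main effect of treatment over five visits, a main effect over weeks 4-16 with week 0 as covariate, and a treatment-by-time interaction. They differ in power and in what a rejection means. With H01, H02 and the contrasts undefined, the choice could be made after the data are seen. The power calculation ought to show which test was planned, and it does not.

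**Working it through.** **Inputs from 6.2.** N = 68 (34 per arm), f = 0.4 (so d = 2f = 0.8 SD between two equal arms), five repetitions, correlation rho = 0.8, nominal alpha 0.05.

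**Assumptions of this check.** Equal correlation between all visits, SD 1, 68 complete cases; rho = 0.5 as a second value; an effect on weeks 4, 8, 12 that is either constant (1, 1, 1) or grows linearly (1/3, 2/3, 1), times d; a week-16 effect that is null or full. Linear growth is prompted by 3.5, which says of the osteoarthritis trial it follows: "This improvement was even more notable at 8 and 12 weeks than at 4".

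**1. The plan's own figure.** Noncentrality = 68 × 0.16 × 5/(1 + 4 × 0.8) = 54.4/4.2 = 12.95. With df (4, 63) and alpha 0.0495, power is 0.802, as printed. This noncentrality equals 17 × 0.8²/0.84, where 0.84 = (1 + 4 × 0.8)/5 is the variance of a five-visit mean. It is therefore that of a between-group average, whose df for two arms are (1, 66); power is then 0.94 at alpha 0.05. It also takes 0.8 SD as the difference averaged over all five visits. With week 0 at zero, a constant on-treatment effect would have to be 0.8/0.8 = 1.00 SD (week 16 full) to 0.8/0.6 = 1.33 SD (week 16 null).

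**2. Unadjusted five-visit main effect, constant effect.** The average is (0+1+1+1+0)/5 = 60% or (0+1+1+1+1)/5 = 80% of the on-treatment effect.
- Week 16 null: 17 × 0.48²/0.84 = 4.66, power 0.57.
- Week 16 full: 17 × 0.64²/0.84 = 8.29, power 0.81.
- Weeks 4-12 only, unadjusted: variance (1 + 2 × 0.8)/3 = 0.867; 17 × 0.64/0.867 = 12.55, power 0.94.
- Weeks 4-12 adjusted for week 0: variance 0.867 − 0.64 = 0.227; 10.88/0.227 = 48, power above 0.99.
- At rho = 0.5 the four values are 0.71, 0.92, 0.98 and above 0.99.

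**3. The same test, linear growth, rho = 0.8.** The five-visit average is 0.4 or 0.6 of the week-12 effect. Power is 0.30 (week 16 null) or 0.57 (full). The fair comparator is weeks 4-12 unadjusted under the same growth: 17 × 0.533²/0.867 = 5.58, power 0.64. Including weeks 0 and 16 therefore costs 0.64 to 0.30, or 0.64 to 0.57. The rest of the gap from 0.94 comes from the assumed growth.

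**4. Week 0 as covariate, weeks 4-16 as four responses.** The variance is (1 + 3rho)/4 − rho², which is 0.21 at rho = 0.8 and 0.375 at rho = 0.5. The worst profile (linear, week 16 null) has mean effect 0.4: 17 × 0.16/0.21 = 12.95, power 0.94; 17 × 0.16/0.375 = 7.25, power 0.76.

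**5. Treatment-by-time, df (4, 63).** Noncentrality = 17 × (sum of squared deviations of the five visit effects from their mean)/(1 − rho). Power is above 0.99 at rho = 0.8 and 0.90-0.99 at rho = 0.5. For a difference of 0.4 SD at week 16 only (illustrative): 17 × 0.128/0.2 = 10.88, and the test rejects with probability 0.72 (0.32 at rho = 0.5). A baseline-adjusted contrast of weeks 4-12 gives week 16 no weight and stays near 5%.

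**6. Candidate contrasts adjusted for week 0, df (1, 65).** Noncentrality = 17d²/V. Each cell gives rho = 0.8 / 0.5.

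| Contrast | V | d for 80% power | Power at d = 0.4, constant | Power at d = 0.4, linear |
|---|---|---|---|---|
| Week 12 | 0.36 / 0.75 | 0.41 / 0.60 | 0.77 / 0.47 | 0.77 / 0.47 |
| Mean of weeks 8 and 12 | 0.26 / 0.50 | 0.35 / 0.49 | 0.89 / 0.63 | 0.76 / 0.48 |
| Mean of weeks 4-12 | 0.227 / 0.417 | 0.33 / 0.445 | 0.93 / 0.71 | 0.62 / 0.39 |

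The d for 80% power is the effect on the contrast itself. The value d = 0.4, half the plan's effect, is chosen here for illustration. At d = 0.8 all three contrasts have at least 0.92 for both shapes and both correlations.

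**The case against.** A reader might infer that the plan averages all five visits and is therefore underpowered. The documents do not support that. Section 6.1 lists the visits as separate nominal levels and does not pool them. The method is called an analysis of covariance, so week 0 may be the unnamed covariate. Contrasts after rejection of H02 suit a time or treatment-by-time hypothesis better than a two-arm main effect. The dilution is thus conditional on an unadjusted main effect, which may not be the intended test. That condition is not met by adding covariates of another kind: adjusting for the gender, age, height or weight in 6.1 would leave the 60-80% ratio unchanged.

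Nor can one infer from df (4, 63) that treatment-by-time was powered. The same df arise as (5 − 1, 68 − 5) in a between-subject test of five groups, and the noncentrality has the between-subject form.

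The week-16-only scenario is contrived. A rejection there would reflect a real difference between arms, not a false positive, and later contrasts could locate it. The Protocol Summary and 3.6.1 also treat week 16 as follow-up. All of this stands. But 6.1 and 6.3 do not carry that distinction into the analysis, and the contrasts that would reveal it are not prespecified.

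**Conclusion.** The point holds in conditional form and should be fixed. Two parts are unconditional: the treatment hypothesis, covariate and on-treatment contrast are undefined, and the printed 0.80 is the power of neither two-group test. The loss itself depends on the reading. It is serious for an unadjusted five-visit main effect if the week-16 effect is gone (0.57 for a constant effect, 0.30 for linear growth), and modest under linear growth if that effect is fully kept (0.57 against 0.64). With week 0 as covariate it is small at rho = 0.8, though power can fall to 0.76 at rho = 0.5. For treatment-by-time the problem is interpretation, not power. The figures rest on complete cases and equal correlations, whereas 3.6 plans carry-forward for missing data. A correlation with week 0 below 0.8 is plausible, because week 0 follows a naproxen washout (3.6.7).

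**What to change.** In 6.1 and 6.3, use weeks 4, 8 and 12 as responses with the week-0 value as covariate, or an equivalent constrained-baseline model that keeps week 0 as a level. Define H01 and H02 so that the treatment hypothesis is one prespecified on-treatment contrast: week 12, the mean of weeks 8 and 12, or the week 4-12 average. Report week 16 as a separate off-treatment secondary contrast. In 6.2, replace the 0.80 with the power of the chosen contrast at df (1, 65).

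On the choice: week 12 is the least sensitive to the shape of the effect; the week 4-12 average has the most power for a constant effect; weeks 8 and 12 together are a compromise consistent with the time course cited in 3.5.

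The cost is text edits and a redone power calculation, since the current one assumes five repetitions. All the data are already collected under the visit schedule. The downside is some power lost if the contrast does not match the effect's shape, as the d = 0.4 columns show. The change does not settle which of the three outcomes is primary, or the carry-forward rule.

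### The power output in 6.2 is that of a five-group test, not of the two randomised groups, and the powered effect is not named

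*Combined protocol and SAP*

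**What the plan says.** The design has two arms. The brief summary says "Subjects will be randomized into 1 of 2 groups", and 6.1 lists "Treatment: nominal variable (Naproxen + MSM, Naproxen + placebo" as the treatment factor. Section 6.1 also lists "Time (5 repeated measures for each subject): nominal variable (0wk, 4wk, 8wk, 12wk, 16wk", so week 0 is one of the five repeated measures. Week 16 is another, although the Visit 4/Week 12 heading in 3.6 notes "SUBJECTS STOP TAKING STUDY PILLS AT THIS VISIT".

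Section 6.2 gives the power for the rANCOVA and concludes that "34 subjects per Treatment group with 5 repeated measures will achieve a power of 0.80 to detect a large effect size of 0.40". Its inputs are "Effect size f = 0.4", "β/α ratio = 4", total sample size 68, 2 groups, 5 repetitions and a correlation of 0.8. Its outputs are critical F 2.524097, df 4 and 63, alpha 0.049538, beta 0.198150 and power 0.801850. The effect size is justified by one sentence: "The investigators anticipate there will be large effect size as determined by a 50% improvement in clinical outcomes". No outcome, mean difference or SD is given.

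Section 6.3 refers to H01 and H02 without defining them. Section 6.4 plans 100 enrolled so that 68 complete.

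**The concern.** For two groups, a between-group comparison has 1 numerator df, not 4. Four numerator df point either to five groups or to a test across five visits. Section 6.2 does not say whether it powers the treatment effect averaged over visits or the treatment-by-time interaction, so the output cannot be matched to a hypothesis by reading the text.

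The block is the only support for 68 completers and hence for enrolling 100. If its outputs do not follow from its inputs, the reader does not know which effect, or what size of difference, the trial has 80% power to detect. That matters most when a null result has to be interpreted.

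**Working it through.** **Inputs (all from 6.2).** f = 0.4, N = 68, k = 2 groups, m = 5 repetitions, rho = 0.8, beta/alpha = 4. With a fixed ratio, alpha is an output: the critical F is the value at which beta = 4 × alpha.

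**Step 1. Reproduce the printed output.** For a between-group effect in a repeated-measures design,

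lambda = f² × N × m / (1 + (m − 1) × rho) = 0.16 × 68 × 5 / (1 + 4 × 0.8) = 54.4 / 4.2 = 12.952, with df k − 1 and N − k.

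Solving for beta = 4 × alpha at different numbers of groups:

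| Groups | df | Critical F | alpha | Power |
|---|---|---|---|---|
| 2 | 1, 66 | 5.2744 | 0.0248 | 0.901 |
| 3 | 2, 65 | 3.5370 | 0.0348 | 0.861 |
| 4 | 3, 64 | 2.8790 | 0.0427 | 0.829 |
| 5 | 4, 63 | 2.524097 | 0.049538 | 0.801850 |
| 6 | 5, 62 | 2.2993 | 0.0556 | 0.778 |

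Five groups reproduces every printed digit. The printed input of two groups does not.

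**Step 2. Can two groups give the same output by another test?** A multivariate five-visit test (time or treatment-by-time) with two groups has df m − 1 = 4 and N − k − (m − 1) + 1 = 68 − 2 − 4 + 1 = 63, the printed df. Its lambda at the same f is f² × N × m / (1 − rho) = 54.4 / 0.2 = 272, and its power exceeds 0.999. If f were instead defined so that lambda = f² × N = 10.88, the power would be 0.753 with ratio 4, or 0.721 at alpha 0.05. Neither is 0.801850.

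**Step 3. The two-group treatment effect at the printed inputs.** F(1,66) with lambda 12.952 gives 0.901 with ratio 4 (alpha 0.0248). At alpha 0.05 the critical F is 3.986 and the power 0.944. With two equal groups f = d/2, so f = 0.4 means d = 0.8 SD in the average over all five visits, week 0 included.

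**Step 4. Allow for no difference at week 0.** For the five-visit average, lambda = (d/2)² × 68 × 5 / 4.2, tested at alpha 0.05.

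- 0 at week 0 and 0.8 SD at weeks 4 to 16: average 0.8 × 4/5 = 0.64 SD, lambda 0.32² × 340 / 4.2 = 8.29, power 0.81.
- Power 0.80 needs lambda 8.084, so average d = 2 × √(8.084 × 4.2 / 340) = 0.632 SD. That is 0.632 × 5/4 = 0.79 SD at each of weeks 4 to 16. If rho is allowed to range from 0.5 to 0.9 (an assumption), the average is 0.534 to 0.661 SD.
- 0.8 SD at weeks 4 to 12 only (an assumption): average 0.8 × 3/5 = 0.48 SD, lambda 4.66, power 0.57.

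**Step 5. Treatment-by-time.** With 34 per group and equal correlations, lambda = (68/4) × (sum of squared deviations of the visit differences from their mean) / (1 − rho), on F(4,63).

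- 0 at week 0 and d at weeks 4 to 16: the sum of squares is 0.8d², so lambda = 17 × 0.8d² / 0.2 = 68d². Power 0.80 at alpha 0.05 needs lambda 12.865, so d = √(12.865 / 68) = 0.435 SD. Rounding down to 0.43 gives lambda 12.57 and power 0.790. At rho = 0.5 (an assumption), d would be 0.688 SD.
- 0.8 SD at weeks 4 to 12 only: the sum of squares is 0.768, lambda = 17 × 0.768 / 0.2 = 65.3, power above 0.999.

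**The case against.** The best defence starts from the df. Values of 4 and 63 are correct for a two-group, five-visit multivariate test, and 6.3 allows contrasts only after H02 is rejected, which hints that H02 concerns more than two means. Both points stand, so the df alone prove nothing. What fails is the combination: with those df and the printed f, lambda is 272, and the printed critical F, alpha and power do not follow.

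A second defence is that the consequence is modest. This also stands. At the printed f the two-group treatment test has more power than claimed, so a reader who infers from the mismatch that 68 is too few goes beyond the documents.

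The 0.57 in step 4 could likewise be read as the trial's true power. It is not. It belongs to an unadjusted average of all five visits under an assumed loss of effect by week 16. For the same pattern, treatment-by-time has power above 0.999. The plan names an analysis of covariance but lists no covariates, so the unadjusted average is only one possible reading.

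Finally, 3.6 provides for intention-to-treat analysis with carry-forward, so the number analysed could approach 100. Taking imputed values at face value, N = 100 would raise the 0.64 SD case from 0.81 to 0.93 and the 0.48 SD case from 0.57 to 0.74. The replacement figures below are therefore tied to 68 completers, the basis that 6.2 and 6.4 use.

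**Conclusion.** The block in 6.2 is wrong as written. Its outputs match a five-group between-subject test to every printed digit, while its own input and the design say two groups. None of the two-group tests checked gives both the printed df and the printed power. For the treatment effect at the printed inputs, the stated 0.80 should be 0.901 (ratio 4) or 0.944 (alpha 0.05). The latter presumes 0.8 SD even at week 0, so it is not a realistic power for the trial.

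A reader might infer that the number of repetitions was also entered as the number of groups. That would explain the match, but the documents do not show how the slip arose. The second defect is independent of the first: the powered effect is unnamed, H01 and H02 are undefined, and f = 0.40 cannot be derived from a 50% improvement without a mean difference and an SD.

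This should be fixed. The sample-size justification is invalid as printed, but nothing here shows that N = 68 is wrong. The replacement figures assume equal correlations of 0.8, no difference at week 0 and alpha 0.05.

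**What to change.** Keep 68 completers. In 6.2, name the powered effect, tie it to H01 or H02, and replace the block with a two-group calculation at alpha 0.05 whose df and lambda belong to that effect:

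- **Treatment effect averaged over five visits.** Two groups of 34, rho 0.8, F(1,66), critical F 3.986. Power is 0.80 for an average difference of 0.63 SD, which is 0.79 SD at each of weeks 4 to 16 when the week-0 difference is zero. Do not print 0.944 as the trial's power. If 0.57 is quoted for an effect of 0.8 SD at weeks 4 to 12 only, label it as applying to the unadjusted five-visit average.
- **Treatment-by-time.** F(4,63). With zero at week 0, a constant d at weeks 4 to 16 and equal correlations of 0.8, lambda = 68d² and power is 0.80 for d = 0.435 SD.

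Delete the claim that f = 0.40 is determined by a 50% improvement unless a mean difference and SD are supplied.

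The cost is text in 6.2 and the definitions of H01 and H02 in 6.3. The target of 68 completers and the visit schedule do not change.
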